Adverse Event Collection/ CTCAE Grading		Х	Х		Х	Х	Х	Х	Section 8.3	 Collect continuously at every visit and throughout the study CTCAE Version 5.0 For long-term follow-up: all SAEs regardless of relationship to study treatment and adverse events possibly related to study treatment will be collected All adverse events possibly related to study drugs or protocol procedures should be followed until they resolve, are no longer considered to be possibly related, become stable or return to baseline, the patient starts a new therapy, the patient expires, or the patient becomes lost to follow-up. The frequency of evaluation is determined according to the judgment of the investigator
Concomitant Medications		Х	x		Х	х	Х		Section 6.5	 At baseline, record prior and concurrent medications Record all pre-medications, supportive care, and concomitant medication continuously at every visit and throughout study
Lab/Diagnostic Tests	Coagulation	Х							Section 10.4 Appendix 4	 Perform at baseline and as clinically indicated Local testing

	Study Period	Baseline	Stu	Study Treatment (Cycle =28 day				ontinuation ow-Up		
	Cycle	Screening	1 a	nd 2	3	4 and Beyond (if Applicable)	Short-Term Follow-Up ^a	Long-Term Follow-Up ^a		
	Visit	0	1,3	2, 4	5	6 and Beyond (if Applicable)	801	802–8XX		
	Relative Day within a Cycle	≤28	Day 1	Day 15° (± 3)	Day 1 (± 3)	Day 1 (± 3)	Day 30 (± 7)	(± 14)		
Procedure Category	Procedure								Protocol Reference	Instructions
	Hematology	Х	Х	х	X	X	Х		Section 10.4 Appendix 4	 Assessments may be performed up to 3 days prior to Day 1 of each cycle Local testing Cycles 1 and 2 Day 15 hematology required for Arms A, C only
	Clinical chemistry	Х	х	x	Х	х	Х		Section 10.4 Appendix 4	 Assessments may be performed up to 3 days prior to Day 1 of each cycle Central testing Cycles 1 and 2 Day 15 clinical chemistry required for Arms A, C only
	FSH and estradiol levels	x				х	Х		See Section 5.1 and Section 10.4	 For Screening: local FSH/E2 testing for women <60 years when needed to confirm post-menopausal status For On study: local estradiol every 3 cycles, starting on Day 1 of Cycle 4 and again at STFU visit, for women whose postmenopausal status is due to GnRH agonist treatment
	Pregnancy test	Х					Х		Section 10.7 Appendix 7	 Local testing For Screening: serum pregnancy test required for women of child-bearing potential For on Study: per local regulations and/or institutional guidelines For Short-Term Follow-Up: local testing for women of child bearing potential

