6.6. Dose Modification

General Considerations for Dose Delays.

In addition to the permitted protocol windows (see Schedule of Activities, Section 1.3), treatment cycles may be delayed up to 7 days due to holidays, weekends, bad weather, or other unforeseen circumstances and will not be deemed a protocol violation.

In exceptional cases, for planned delays (including but not limited to vacation or holidays), additional study drug may be dispensed.

When a study drug is delayed, if possible and appropriate, patients should resume study treatment within 1 treatment cycle and, if not possible, then every effort should be made to start on the first day of the next dosing cycle. In rare circumstances, a delay of >28 days may be permitted before permanent treatment discontinuation, as long as the patient has clinical benefit without objective disease progression and is recovering from the toxicity. Such circumstances must be discussed with the Sponsor CRP/CRS. All dose modifications should be documented, including the approach taken and a clear rationale for the need for modification.

Dose Modifications for Imlunestrant

Management of some adverse reactions may require dose interruption and/or dose reduction. If dose reduction is necessary, decrease the dose by 200 mg. Discontinue imlunestrant for patients unable to tolerate 200 mg QD. In the event that imlunestrant must be discontinued, a participant may continue to receive abemaciclib (Arm C only).

Refer to the tables below for further details on dose modification and management.

Dose Adjustment	Oral Dose Imlunestrant	Frequency
0	400 mg	QD
1	200 mg	QD

Table 1: Imlunestrant Dose Reduction Guidelines

Abbreviation: QD = once daily.

6.6.1. Imlunestrant Dose Adjustments for Treatment-Emergent, Related*, and Clinically Significant Adverse Events

Treatment-emergent laboratory abnormalities of neutrophil count decreased and/or ALT/AST increased, regardless of clinical significance, must follow the dose adjustment table below.

*Related means there is a reasonable causal relationship with imlunestrant.

Toxicity Type	Toxicity Profile and Severity	Dose Suspension	Dose Reduction
Hematologic	Grade 3	Dose MUST be suspended until toxicity resolves to at ≤Grade 2	Not required
toxicity	Grade 4 or Recurrent Grade 3	Dose MUST be suspended until toxicity resolves to at ≤Grade 2	Resume at next lower dose level

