If Patient Requires Administration of Blood Cell Growth Factors	Regardless of severity	Dose MUST be suspended until toxicity resolves to at least Grade 2 and a minimum of 48 hours after growth factor administration	Resume at next lower dose unless the dose was already reduced for the toxicity that led to the use of the growth factor (that is, second dose reduction not required)
Febrile neutropenia	Regardless of severity	Dose MUST be suspended until toxicity resolves	Resume at next lower dose level
Nonhematologic toxicity (except diarrhea, alopecia, and	Persistent or recurrent Grade 2 that does not resolve with maximal supportive measures within 7 days to baseline or Grade 1	Dose MUST be suspended until toxicity resolves to baseline or Grade 1	Not required
hepatotoxicity) ^a	Grade 3 or 4 (except non- hepatic asymptomatic laboratory changes)	Dose MUST be suspended until toxicity resolves to baseline or Grade 1	Resume at next lower dose level
	AST/ALT >ULN - 5.0×ULN	Not required	
Hepatotoxicity	Persistent or Recurrent: AST/ALT >3.0-5.0×ULN	Dose MUST be suspended until toxicity resolves to baseline or to >ULN- 3.0×ULN	Not required

Toxicity Type	Toxicity Profile and Severity	Dose Suspension	Dose Reduction	
	AST/ALT >5.0-20×ULN Or ALT or AST \geq 3 × baseline (if ALT or AST \geq 1.5 × ULN at baseline) or AST/ALT >8 × ULN (whichever is the lower threshold)	Dose MUST be suspended until toxicity resolves to baseline or to ALT/AST>ULN - 3.0×ULN	Resume at next lower dose level	
	AST/ALT >20.0×ULN Or			
	ALT or AST \ge 3 × ULN concurrent with TBL \ge 2 × ULN (if ALT or AST < 1.5 × ULN at baseline), in the absence of cholestasis	Discontinue imlunestrant		
	Or ALT or AST $\geq 2 \times$ baseline concurrent with TBL $\geq 2 \times$ ULN (if ALT or AST $\geq 1.5 \times$ ULN at baseline), in the absence of cholestasis			
	Grade 1	Not re	quired	
	Grade 2 that does not resolve with maximal supportive measures within 24 hours to ≤Grade 1	Suspend until toxicity resolves to ≤Grade 1	Not required	
Diarrhea	Grade 2 that persists or recurs after resuming the same dose despite maximal supportive measures. Requires hospitalization or Grade 3 or 4	Suspend until toxicity resolves to ≤Grade 1	Resume at next lower dose level	
Bloody diarrhea	Any grade	Dose MUST be suspended until bloody diarrhea resolves and diarrhea resolves to Grade ≤1	Resume at next lower dose level	

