8.2.2. Clinical Safety Laboratory Assessments

See Appendix 4 (Section 10.4) for the list of clinical laboratory tests to be performed and see the SoA (Section 1.3) for the timing and frequency.

The investigator must review the laboratory report, document this review, and record any clinically relevant changes occurring during the study in the AE section of the CRF. The laboratory reports must be filed with the source documents. Clinically significant abnormal

laboratory findings are those which are not associated with the underlying disease, unless judged by the investigator to be more severe than expected for the patient's condition.

All laboratory tests with values considered clinically significantly abnormal during participation in the study or until the completion of Visit 801 after the last dose of study intervention should be repeated until the values return to normal or baseline or are no longer considered clinically significant by the investigator or medical monitor.

- If such values do not return to normal/baseline within a period of time judged reasonable by the investigator, the etiology should be identified, and the Sponsor notified.
- All protocol-required laboratory assessments, as defined in Appendix 4 (Section 10.4), must be conducted in accordance with the laboratory manual and the SoA (Section 1.3).

If there is an abnormal laboratory value or abnormal value for any other diagnostic or screening test (for example, blood pressure increased, neutrophils decreased) and it is known to be related to a disease diagnosis (for example, hypertension, neutropenia), this should be reported in the CRF as an AE. Do not enter the test abnormality; enter the disease diagnosis or categorical term. If laboratory values from non-protocol-specified laboratory assessments performed at the institution's local laboratory require a change in patient management or are considered clinically significant by the investigator (for example, SAE or AE or dose modification), then the event(s) must be reported in the CRF as AEs.

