8.2.2.1. Hepatic Safety Monitoring

Liver testing (Section 10.9 Appendix 9), including ALT, AST, alkaline phosphatase, TBL, direct bilirubin, gamma-glutamyltransferase, and creatine phosphokinase, should be repeated (local testing acceptable) within 2 to 4 days to confirm the abnormality and to determine if it is increasing or decreasing, if 1 or more of these conditions occur:

In participants with baseline ALT or AST <1.5 ULN

- Elevation of serum ALT or AST to $\geq 5 \times$ ULN
- The combination of elevated ALT or AST $\ge 3 \times$ ULN and elevated TBL $\ge 2 \times$ ULN

In participants enrolled with baseline ALT or AST $\geq 1.5 \times$ ULN

- Elevated ALT or AST $\geq 3 \times$ baseline
- The combination of elevated ALT or AST $\geq 2 \times$ baseline and elevated TBL $\geq 2 \times$ ULN

If the abnormality persists or worsens, clinical and laboratory monitoring and evaluation for possible causes of abnormal liver tests should be initiated by the investigator in consultation with the Sponsor-designated medical monitor. At a minimum, this evaluation should include physical examination and a thorough medical history, including symptoms, recent illnesses (for example, heart failure, systemic infection, hypotension, or seizures), history of concomitant medications (including over-the-counter, herbal, and dietary supplements), history of alcohol drinking and other substance abuse. In addition, the evaluation should include a blood test for PT-INR; serological tests for viral hepatitis A, B, C, E, autoimmune hepatitis; and an abdominal imaging study (for example, ultrasound or CT scan).

Based on the patient's history and initial evaluation results, further testing should be considered, in consultation with the Sponsor-designated medical monitor, including tests for hepatitis D

virus, cytomegalovirus, Epstein-Barr virus, acetaminophen levels, acetaminophen protein adducts, urine toxicology screen, Wilson's disease, blood alcohol levels, urinary ethyl glucuronide, and serum phosphatidylethanol. Based on the circumstances and the investigator's assessment of the participant's clinical condition, the investigator should consider referring the participant for a hepatologist or gastroenterologist consultation, magnetic resonance cholangiopancreatography, endoscopic retrograde cholangiopancreatography, cardiac echocardiogram, and/or a liver biopsy.

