For patients that meet the criteria above, whenever possible and as clinically appropriate, continue monitoring after discontinuation of imlunestrant until values are back to baseline.

Additional Hepatic Safety Collection

Additional safety data outlined in Section 10.9 Appendix 9 should be collected via the CRF if 1 or more of the following conditions occur:

In participants with baseline ALT or AST <1.5 ULN

- Elevation of serum ALT or AST to $\geq 5 \times$ ULN on 2 or more consecutive blood tests
- The combination of elevated ALT or AST $\ge 3 \times$ ULN and elevated TBL $\ge 2 \times$ ULN

In participants enrolled with baseline ALT or AST $\geq 1.5 \times$ ULN

- Elevated ALT or AST $\geq 3 \times$ baseline on 2 or more consecutive tests
- The combination of elevated ALT or AST $\geq 2 \times$ baseline and elevated TBL $\geq 2 \times$ ULN

In all study participants

- discontinuation from study treatment due to a hepatic event or abnormality of liver tests
- occurrence of a hepatic event considered to be a SAE.

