10.17. Appendix 17: Protocol Amendment History

The Protocol Amendment Summary of Changes Table for the current amendment is located directly before the Table of Contents (TOC).

Amendment [c]

This amendment is considered to be nonsubstantial.

Overall Rationale for the Amendment:

The primary purpose of this amendment is to increase the sample size for PFS between Arm A and Arm B (for the first two primary endpoints). Changes are outlined in this table.

Section # and Name	Description of Change	Brief Rationale
Section 1.1. Synopsis	Updated to match changes in the main protocol	Update
Section 1.2. Schema	Removed the footnote addressing Arm B enrollment.	Arm B is now wider, so the schema shows all study arms will close at the same time.
Section 1.3. Schedule of Activities	Clarified short-term and long-term follow-up visit day; clarified footnote "a" and included details of Cycle 2 Day 15 under Foot note "c"	Correction
	Added text to second instructional comment for Bone scintigraphy line item: "start of a new anticancer therapy"	For consistency with radiologic imaging
Section 2. Introduction	Added Introduction/Rationale for Amendment (c)	Addition
Section 3. Objectives and Endpoints	Added row under exploratory analysis: "To assess clinical efficacy parameters of Arm C compared to Arm B" for endpoints PFS and OS	Updates to study design
Section 4.1. Overall Design; Section 6.3. Measures to Minimize Bias: Randomization and Blinding	Clarified language regarding randomization into Arm A, B, and C; updated language regarding analysis of PFS	Updates to study design
Section 5.1. Inclusion Criteria	Criterion 3: Additional notes added to better understand criterion #3 in a global study without any changes in actual eligibility criterion. Criterion 5: removed "and FSH" from note	Clarification

Section # and Name	Description of Change	Brief Rationale
Section 6.6.1. Imlunestrant Dose Adjustments for Treatment-Emergent, Related, and Clinically Significant Adverse Events	Included AST/ALT >8 x ULN under toxicity profile and severity for hepatotoxicity	Clarification
Section 6.1. Study Intervention(s) Administered	Edited fulvestrant paragraph, removing specific language for "1 to 2 minutes per injection," and referenced approved label Added text to exemestane paragraph;	Clarification
	referred to approved label	

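### For patients whose ALT and AST are both raised at baseline, the 2-4 day liver retest trigger in Section 8.2.2.1 lacks the >8×ULN limb of the imlunestrant suspension row in Section 6.6.1

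*Protocol*

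**What the plan says.** Inclusion criterion 10 (Protocol Section 5.1) allows ALT and AST up to 3×ULN at entry.

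Section 6.6.1 makes its table binding for ALT/AST increases, which "regardless of clinical significance, must follow the dose adjustment table below". The suspend-and-reduce row for hepatotoxicity holds three limbs in one cell: above 5.0 and up to 20×ULN; at least 3×baseline if baseline was at least 1.5×ULN; or "AST/ALT >8 × ULN (whichever is the lower threshold". Dosing then resumes one level lower, which from the starting dose means 200 mg. The history of amendment (c) in Appendix 17 records the origin of the last limb: "Included AST/ALT >8 x ULN under toxicity profile and severity for hepatotoxicity".

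Section 8.2.2.1 says that, once a trigger is met, liver tests "should be repeated (local testing acceptable) within 2 to 4 days to confirm the abnormality and to determine if it is increasing or decreasing". The triggers depend on baseline:

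- Baseline ALT or AST below 1.5×ULN: a value of at least 5×ULN.
- Baseline ALT or AST at least 1.5×ULN: a value of at least 3×baseline.

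Each group also has a combined trigger with bilirubin at or above 2×ULN. The next steps follow from the retest: "If the abnormality persists or worsens, clinical and laboratory monitoring and evaluation for possible causes of abnormal liver tests should be initiated". The hepatic CRF pages use the same thresholds; for an isolated rise from a raised baseline they need at least 3×"baseline on 2 or more consecutive tests".

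**The concern.** The two sections deal with the same laboratory event, but only one has a ceiling in absolute ULN terms for patients who start high. In Section 6.6.1 a raised baseline cannot push the suspension threshold beyond 8×ULN. In Section 8.2.2.1 the retest threshold rises with baseline without limit, reaching 9×ULN for a patient admitted at 3×ULN. A value can therefore be serious enough to force suspension and a dose reduction yet not start the 2-4 day check on whether it is rising or falling. The structured evaluation and the hepatic CRF pages carry the same baseline-relative threshold, so they can be missed too. What is at stake is the timing and completeness of liver follow-up in a small group, not efficacy inference.

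**Working it through.** The plan states no figure to reproduce here; the check is threshold arithmetic.

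**Inputs.** Let b be baseline in ×ULN, with b ≤ 3 (Section 5.1). For b ≥ 1.5 the isolated-rise retest starts at 3b (Section 8.2.2.1). The suspension limbs are >5, ≥3b and >8×ULN (Section 6.6.1). *Isolated* means bilirubin below 2×ULN; otherwise the combined trigger at 2×baseline applies.

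**Two readings of the suspension row for b ≥ 1.5**

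- Literal: the >5×ULN limb has no baseline condition and applies to everyone, so suspension starts at the lower of 5 and 3b. The >8×ULN limb then never acts.
- Restrictive: raised baselines use only the lower of 3b and 8. This gives the >8×ULN limb a function, but the row does not say it.

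**Where a gap opens.** A gap exists when 3b exceeds the suspension threshold.

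- Literal: 3b > 5, so b > 5/3 = 1.67.
- Restrictive: 3b > 8, so b > 8/3 = 2.67.

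| b (×ULN) | Retest from 3b | Suspended without retest, literal | Suspended without retest, restrictive |
|---|---|---|---|
| 1.5 | 4.5 | none | none |
| 2.0 | 6.0 | >5 to <6 | none |
| 2.5 | 7.5 | >5 to <7.5 | none |
| 2.8 | 8.4 | >5 to <8.4 | >8 to <8.4 |
| 3.0 | 9.0 | >5 to <9 | >8 to <9 |

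Any value above 8 is also above 5, so the last column holds under either reading.

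**Example.** With b = 3.0 and ALT 8.5×ULN, the ratio is 8.5/3.0 = 2.83×baseline. Suspension and reduction are mandatory under both readings. The retest trigger of 9.0×ULN is not met.

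**Time to the next fixed test.** If the retest is triggered, it falls at 2-4 days. If not, the Schedule of Activities (Section 1.3) governs: "Cycles 1 and 2 Day 15 clinical chemistry required for Arms A, C only", plus Day 1 of each cycle. The nominal wait is up to 15 − 1 = 14 days in Cycles 1-2 and up to 28 days from Cycle 3.

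**Mixed baselines.** A patient with one enzyme below and one at or above 1.5×ULN also fits the wording of the lower-baseline group, and so may be retested from 5×ULN. The gap is clear only when both enzymes start at 1.5×ULN or more.

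**The case against.** The strongest reply is that the two sections do different jobs. Section 6.6.1 manages dose, largely in absolute ULN terms. Section 8.2.2.1 starts a liver-injury work-up and scales to baseline because a raised starting value makes absolute multiples less informative. A rise from 3.0 to 5.5×ULN is only 5.5/3.0 = 1.8×baseline, and with drug held a sponsor could reasonably leave that to judgment. This has force against the wider literal-reading gap. It has less force above 8×ULN, where the sponsor itself put an absolute ceiling into the dosing rule.

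The second reply is that follow-up exists elsewhere, and this largely stands. Section 8.2.2 requires clinically significant values to be repeated; if they do not normalise in reasonable time, "the etiology should be identified, and the Sponsor notified". Resuming drug requires evidence of recovery, hence a repeat ALT/AST. Appendices 4 and 9 permit extra and local testing. But the first depends on a judgment of clinical significance, which Section 6.6.1 sets aside for dosing. The appendix tests are discretionary, and none of these routes has a 2-4 day clock.

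Two stronger readings are tempting. A reader might infer that these patients stay on drug or go without liver follow-up; the documents say otherwise on both counts. A reader might also infer that the 6.6.1 row is contradictory and that the restrictive reading should replace it. As printed, the >5×ULN limb suspends everyone. That makes the >8×ULN limb redundant, which is not a conflict, and it errs toward earlier suspension. Adopting the restrictive reading would move suspension at baseline 3.0 from >5 to >8×ULN, which is less protective.

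**Conclusion.** The point holds as a minor safety-monitoring mismatch. Under either reading of Section 6.6.1, an isolated ALT/AST value above 8×ULN but below 3×baseline forces suspension and reduction without the fixed retest, for baselines above 2.67 and up to 3×ULN. That window is at most 1×ULN wide. If the >5×ULN limb applies to everyone, the window starts at 5×ULN and covers baselines above 1.67×ULN; at baseline 3.0 it is 4×ULN wide.

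This assumes that both enzymes are raised at baseline and that bilirubin stays below 2×ULN. What can be missing is the 2-4 day retest and, if the rise would have been confirmed, the structured evaluation and hepatic CRF pages. The documents give neither the baseline ALT/AST distribution nor the rate of such rises, so no patient count can be derived; it is likely to be very small. No endpoint analysis changes.

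**What to change.** In Section 8.2.2.1, for baseline ≥1.5×ULN, set the isolated-rise retest trigger to ≥3×baseline or >8×ULN, whichever is lower. Alternatively, let any ALT/AST value that requires suspension with dose reduction under Section 6.6.1 trigger the retest. The first form closes the gap above 8×ULN; the second closes it under either reading. Carry the same limb into the hepatic CRF trigger, keeping the requirement of two or more consecutive tests.

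Separately, the sponsor should state in Section 6.6.1 whether the >5.0-20×ULN limb applies at baseline ≥1.5×ULN. Until then the printed, more protective suspension above 5×ULN should stand. The thresholds themselves are for the sponsor's hepatic safety group.

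The cost is wording in two protocol sections and a note to sites, with a few extra liver tests, which may be local, and a few more hepatic CRF pages.

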6.6.2. Dose Modifications for Endocrine Therapy of Investigator's Choice

Dose adjustments for control arm ET of exemestane are not allowed.

Dose adjustments for control arm ET of fulvestrant will be determined by the investigator in accordance with the approved product labels. For patients with moderate hepatic impairment (defined as Child-Pugh Class B), including any patient who develops moderate hepatic impairment during study treatment, fulvestrant 250 mg should be administered intramuscularly into the buttock slowly (1 to 2 minutes) as one 250-mg injection.

Dose suspensions \geq 28 days must be discussed with the Sponsor CRP/CRS.

6.6.3. Dose Modifications for Abemaciclib

Management of some adverse reactions may require dose interruption and/or dose reduction. If dose reduction is necessary, decrease the dose by 50 mg at a time. Discontinue abemaciclib for patients unable to tolerate 50 mg BID. In the event that abemaciclib must be discontinued, a patient may continue to receive imlunestrant.

Refer to the tables below for further details on dose modification and management.

Recommended Dose Reduction Guidelines for Abemaciclib

Dose Adjustment	Abemaciclib Dose	Frequency
Starting dose	150 mg	BID
First dose reduction	100 mg	BID
Second dose reduction	50 mg	BID

Abbreviation: BID = twice daily.

The toxicity dose adjustments and delays table below provides guidance for the management of treatment-emergent, related (i.e., with reasonable causal relationship with abemaciclib), AEs. An investigator may suspend or reduce doses without meeting one of the criteria below and this would not be considered a protocol deviation.

Toxicity Type	Severity	Dose Suspension	Dose Reduction
	Grade 1 or 2	Not	required
Hematologic Toxicity	Grade 3	Suspend until toxicity resolves to ≤Grade 2	Not required
	Grade 4 or recurrent Grade 3	Suspend until toxicity resolves to ≤Grade 2	Resume at next lower dose level
If Patient Requires Administration of Blood Cell Growth Factors Additional guidance for use of growth factors is in Section 6.5.1.	Regardless of severity	Suspend until toxicity resolves to at least Grade 2 and a minimum of 48 hours after growth factor administration	Resume at next lower dose unless the dose was already reduced for the toxicity that led to the use of the growth factor (that is, second dose reduction not required)
Nonhematologic Toxicity	Grade 1 or 2	Not	required
Excluding Diarrhea, ALT/AST Increased, Interstitial Lung Disease/Pneumonitis, and VTE (see below) Additional guidance for renal monitoring is in Section 8.2.4 and for VTE Section 8.2.5.	Persistent or recurrent Grade 2 that does not resolve with maximal supportive measures within 7 days to baseline or Grade 1. Grade 3 or 4	Suspend until toxicity resolves to baseline or Grade 1	Resume at next lower dose level
	Grade 1	Not	required
Diarrhea	Grade 2 that does not resolve with maximal supportive measures within 24 hours to ≤Grade 1	Suspend until toxicity resolves to ≤Grade 1	Not required
Additional guidance for diarrhea management is in Section 6.5.2.	Grade 2 that persists or recurs after resuming the same dose despite maximal supportive measures. Requires hospitalization or Grade 3 or 4	Suspend until toxicity resolves to ≤Grade 1	Resume at next lower dose level

Toxicity Type	Severity	Dose Suspension	Dose Reduction
	>ULN-5.0×ULN or 1.5-5.0 × baseline (if baseline ≥1.5×ULN)	Not required	
ALT/AST Increased See Section 8.2.2.1 for additional guidance for hepatic monitoring.	Persistent or recurrent >3.0- $5.0 \times ULN$ (or × baseline if baseline $\geq 1.5 \times ULN$), or > $5.0-20.0 \times ULN$ (or × baseline if baseline $\geq 1.5 \times ULN$)	Suspend until toxicity resolves to baseline or >ULN-3.0×ULN	Resume at next lower dose level
nepatie monitoring.	>3.0×ULN (or × baseline if baseline ≥1.5×ULN)with total bilirubin >2×ULN, in the absence of cholestasis, or >20.0×ULN (or × baseline if baseline ≥1.5×ULN)	Discontinu	ie abemaciclib
VTE	Grade 1 or 2	Not	required
Additional guidance for VTE monitoring is in Section 8.2.5.	Grade 3 or 4	Suspend and treat. Resume when the patient is clinically stable.	Not required
	Grade 1 or 2	Not required	
Interstitial Lung Disease/Pneumonitis Additional guidance for ILD/pneumonitis monitoring is in Section 8.2.6.	Grade 2 that persists or recurs despite maximal supportive measures and does not return to baseline or Grade 1 within 7 days.	Suspend until toxicity resolves to baseline or Grade ≤1	Resume at next lower dose level
	Grade 3 or 4	Discontinu	le abemaciclib

Abbreviations: ALT = alanine aminotransferase; ASCO = American Society of Clinical Oncology; AST = aspartate aminotransferase; CTCAE = Common Terminology Criteria for Adverse Events (NCI 2017); ILD = interstitial lung disease; ULN = upper limit of normal; VTE = venous thromboembolic event.

Note: Determination of persistent events will be at the discretion of the investigator. Recurrent toxicity refers to the same event occurring within the next 8 weeks (as measured from the stop date of the first event. As a general guidance, based on the risk/benefit balance assessment per the investigator, for a patient who experiences a new episode of Grade 3 hematological toxicity after more than 8 weeks following the last episode of the same Grade 3 hematological toxicity, the investigator may consider resuming the participant on the same drug dose should the participant satisfy the following conditions:

- The participant showed stable hematological counts (Grade <2) during that timeframe
- In the absence of any infectious sign or risk factor
- The participant is benefiting from study intervention.

